5.3 Vulnerable Subjects

The study does not intend to enroll children, pregnant women, prisoners, or other vulnerable populations.

5.4 Strategies for Recruitment and Retention

To achieve 44 study participants who complete the pilot, we will need to identify ≈ 300 eligible participants from the electronic health record (EHR) in NYU clinics and plan to enroll and randomize 44 participants. Utilizing support from DataCore and NYU Medical Center Information Technology, we will use SlicerDicer and other Epic tools to review EHR for eligibility. The team will request MCIT DataCore to generate a report identifying potential subjects that meet criteria and have upcoming office visit appointments. The study team, including principal investigator, co-investigators, and research assistants, will have access to the Epic search results and verify eligibility of potential subjects. The search results will include PHI- such as medical record numbers. Patients will then be contacted by phone, email, or MyChart portal using an IRB approved message or script. Subjects will also be approached during office visits to introduce the research project and be invited to participate in the study. In addition, the Clinical and Translational Science Institute (CTSI) Recruitment and Retention Core at NYU will be engaged to provide expert consultation.

Interested and eligible participants that have an upcoming clinic appointment will be met at the visit for consent and enrollment. If no clinic visits are upcoming, participants will be invited for a research only

visit. Participants will meet with a research coordinator to review eligibility and provide informed consent. Informed consent will include specific language regarding laboratory testing for the Olink biomarker panel and a separate consent subsection for participation in providing samples for future research. Study discussion and consenting will occur following a clinic visit in a secure private location in either the outpatient clinics or Clinical and Translational Research Institute of NYU Medical Center. Participant will be randomized to true or sham arm of the trial and baseline blood draw will occur at this clinic visit. Blood will be collected and stored for analysis. Participants will receive partial reimbursement for the initial blood draw, and the remainder of remuneration will be given at the final blood draw/equipment return.

Inclusion of Women and Minorities: Women will be included as study participants (approximately 64% of enrolled participants). Minorities will also be included as study participants. Among NYU Langone Health outpatients, African Americans, Hispanic/Latinx, and Asian outpatients represent 16%, 17%, and 5%, respectively, of the potential pool of study participants.

5.4.1 Use of DataCore/Epic Information for Recruitment Purposes

This study will utilize Epic to identify subjects. We will work with DataCore and NYU Medical Center Information Technology to identify ≈300 eligible participants from the EHR in NYU clinics. We will use SlicerDicer and other Epic tools to review EHR for eligibility. The team will request MCIT DataCore generate a report identifying potential subjects that meet criteria and have upcoming office visit appointments. The study team, including principal investigator, co-investigators, and research assistants, will have access to the EPIC search results and verify eligibility of potential subjects.

Any recruitment information sent by email will utilize Send Safe email.

Once potential subjects have been identified, the study team will notify the treating physician (TP) that they have patients eligible to participate as follows:

- TP has been notified that the study team will contact potential subjects directly, by letter, phone, email, or the MyChart portal etc.

Once contact is made, approved recruitment language will be used to communicate the reason they are being contacted and subjects will be asked if they are interested in participating in this specific study. Should the potential subjects agree, the study team will provide the subjects with information regarding the next steps for participation.

If a subject requests information regarding opting out of further recruitment for all research, subjects will be directed to contact [contact] or [name].

5.5 Study Participation

For the initial clinical visit, participant's participation will last approximately 30 minutes for consent and blood draw. The video visit for equipment set up will require 15 minutes. Daily participation will consist of 5-7 minutes for BP monitoring each morning and evening. The final clinical visit for the post-intervention blood draw will last approximately 10-15 minutes.

5.6 Total Number of Participants and Sites

This pilot study will be conducted at NYU Langone Health Main Campus. Recruitment will end when we have consented and enrolled 74 adults, of which we expect 90% to complete the trial.

5.7 Participant Withdrawal or Termination

5.7.1 Reasons for Withdrawal or Termination

This is a minimal risk study, so we do not expect participants to withdraw for a safety related issue. However, participants are free to withdraw from participation in the study at any time upon request. If patients need to sleep elsewhere than their own bedroom for any unanticipated reason during the trial,

they should notify the research team and study endpoints (exposures and SBP) will be excluded from analyses during this period. Participants that unexpectedly require sleeping 2 or more consecutive nights away from their home (or a total of 7 days altogether) during the study period will need to drop from the study and their data will not be used in analyses. They can re-enroll at a later date.

Reasons for withdrawal may be moving from the area or simply not interested in participating further.

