5.7.2 Handling of Participant Withdrawals or Termination

Participation is voluntary and all study participants may withdraw from the study at any time without penalization. Participants may request removal and destruction of their blood samples from storage for future research without withdrawal from the remainder of the study. Participants may request termination from the study separate from withdrawal from future research.

No replacement of participants who withdraw or discontinue early will occur. Data including date and reason for withdrawal will be recorded.

A participant is considered lost to follow-up after 10 attempts to contact them by phone and 10 attempts by Epic messaging.

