6.1.4 Duration of Therapy

The PACs will be run continuously (24 hours per day) in participants' bedrooms for 4 weeks.

7 Study Procedures and Schedule

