10.2 Analysis Datasets

These analyses will be conducted as Intention-to-Treat dataset. Per-Protocol Analysis will be explored if electricity monitor data indicates poor compliance with PAC usage (if electricity monitor recordings indicate kilowatt-hour usage that is lower than expected by 50%).

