Attachment C: Participant Instructions for Equipment Setup

Equipment Setup Instructions:

You have received:

1. Blood pressure cuff
2. Home Air Cleaner
3. Electricity monitor
4. Data Hub & cord
5. Air Pollution monitor & cord

- Plug the electricity monitor (4) into an outlet in your bedroom/sleeping area.
- Plug the Air Cleaner (2) into outlet number 1 on the electricity monitor.
- Turn the Air cleaner on to level 1. (You will leave it like this for the whole study.)
- Hang the air pollution monitor (5) to a wall on the opposite side of the same room – use the included command hook to secure it to a wall about 4 feet above an outlet.
- Plug in the air pollution monitor.
- Plug in the data hub (3) within 10 feet of where you will check your blood pressure (1). Please see separate instructions for use.

Bring to your final visit:

3. Electricity monitor
4. Data Hub & cord
5. Air Pollution monitor & cord

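### Section 5.7.1 removes randomised participants from the analyses for nights spent away from home, which contradicts the intention-to-treat dataset in 10.2, and it allows re-enrolment without saying how a returning participant is handled.

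*Combined protocol and SAP*

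**What the plan says.** Section 5.4 fixes the time of allocation: "Participant will be randomized to true or sham arm of the trial and baseline blood draw will occur at this clinic visit". The air cleaner is turned on afterwards, within seven days of that draw (7.5).

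Section 5.7.1 then treats unplanned nights away in two steps.

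- For any such absence, "study endpoints (exposures and SBP) will be excluded from analyses during this period".
- Once the absence reaches two nights in a row, or seven days altogether, participants "will need to drop from the study and their data will not be used in analyses. They can re-enroll at a later date".

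Section 10.2 states: "These analyses will be conducted as Intention-to-Treat dataset". It names one route to a per-protocol analysis: poor compliance, judged "if electricity monitor recordings indicate kilowatt-hour usage that is lower than expected by 50" percent. Nights away are not mentioned there.

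Four other places bear on the point.

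- Section 5.7.2: "No replacement of participants who withdraw or discontinue early will occur".
- Section 7.7: the withdrawal visit is for returning equipment, and no blood draw is listed.
- Section 7.6: the final draw takes place four weeks after the device is turned on, and at most 35 days after.
- Section 10.4: baseline-only data from non-completers are to be included.

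**The concern.** An absence from home happens after randomisation. Removing people because of it leaves a subset selected on a post-randomisation event, and an intention-to-treat dataset exists to prevent that. The two sections therefore give different answers to the question of who enters the primary TNFα comparison. At the lower threshold, 2 of 28 nights (7% of the intervention period) remove a participant entirely.

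The loss is also hard to undo. If a dropped participant gives no second sample, no later analysis can restore the value, so the rule has to be settled before it is applied.

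Re-enrolment adds a gap. The documents do not say whether a returning person keeps the first allocation or is randomised again, whether the baseline sample is repeated, or whether the person counts once or twice.

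**Working it through.** **Text comparison.** The main finding needs no figure.

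1. Allocation is at the baseline visit (5.4), so every exclusion for nights away comes after randomisation.
2. The first step in 5.7.1 is limited to exposure and SBP data for the days away. The second step drops that limit and refers to the participant's data without qualification. It therefore covers TNFα, the primary endpoint in 4.2.1.
3. Section 10.2 neither makes an exception nor defines a modified intention-to-treat set that could absorb the rule.
4. The electricity trigger does not cover it either. The device is to run around the clock (6.1.4) on one setting, and Attachment C tells participants "You will leave it like this for the whole study". A device left on in an empty bedroom shows no shortfall. If it were off for the whole absence, at constant power over 28 days, the shortfall would be 2/28 = 7% or 7/28 = 25%. A 50% shortfall needs 14 of 28 days off.

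**Illustrative bias.** The documents give no absence rate and no SD. Assume that a fraction f of one arm only is excluded, and that those excluded differ from those retained by d = 0.5 to 1.0 SD in TNFα change. Bias = f × d. The SE of the difference in SD units is √(1/n₁ + 1/n₂) for those analysed. Type I error uses the normal approximation at two-sided 0.05. Both enrolment totals in the protocol are shown: 44 (10.4) and 74 (5.6).

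| | 2 of 22 excluded | 3 of 37 excluded |
|---|---|---|
| f | 0.091 | 0.081 |
| Bias (SD) | 0.045 to 0.091 | 0.041 to 0.081 |
| SE (SD) | √(1/20 + 1/22) = 0.309 | √(1/34 + 1/37) = 0.238 |
| Bias/SE | 0.147 to 0.294 | 0.171 to 0.341 |
| Type I error | 5.2% to 6.0% | 5.3% to 6.3% |

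If absence is unrelated to arm and outcome, the bias is 0.

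**Cost of retaining them.** If the effect is proportional to nights at home, dilution = f × (nights away / 28).

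- 2 of 22 away 2 nights: 0.091 × 2/28 = 0.6%.
- 2 of 22 away 7 nights: 0.091 × 7/28 = 2.3%.
- 2 of 22 with no effect at all: 2/22 = 9.1%.
- 3 of 22 with no effect at all: 3/22 = 13.6%.

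Applied to the 10% change assumed in 10.4, 0.6 to 2.3% dilution leaves 9.9 to 9.8%.

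**The case against.** The strongest reply is that this is a small pilot with a sham of identical appearance and sound. Arm-related absence is then unlikely, no bias is shown, and even a deliberately one-sided illustration moves the type I error only to about 6%. That stands. The case rests on the contradiction between sections, not on a demonstrated bias.

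A second reply is that retention creates a problem of its own. Aim 2 relates TNFα to PM2.5 measured in the bedroom. For someone away many nights, the home-days average does not describe the exposure that shaped the second TNFα value. This also stands, and the fix has to deal with it.

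Some stronger readings are tempting but not supported.

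- *The no-replacement rule forbids re-enrolment.* Section 5.7.2 concerns replacing people who leave. It is silent on the same person returning, so this is a gap and not a contradiction.
- *The baseline-only sentence in 10.4 alters the primary result.* Its wording is inconsistent with 5.7.1, but a participant with only a baseline value has no change score and cannot enter the model in 10.3. The Aim 1 estimate is unaffected.
- *The loss is already covered by the 10% dropout allowance.* With no absence rate this cannot be known. The allowance matches 66/0.9 = 73.3, rounded up to the 74 in 5.6. The target of 44 is not inflated, since 5.4 wants 44 completers and plans to randomise 44.
- *Dilution cannot exceed 9.1%.* That figure belongs to 2 of 22 with no effect. It rises with the number of people away, as the 13.6% shows.

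**Conclusion.** The contradiction is definite. Under 5.7.1 the primary TNFα analysis would not be the intention-to-treat analysis that 10.2 announces, and the second TNFα sample would usually be lost. The handling of re-enrolled participants is unspecified.

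A reader might infer that the trial's result will be biased. The documents do not support that: bias may be zero, and the blinded sham makes arm-related absence less likely. The figures of 0.04 to 0.09 SD bias and 5.2 to 6.3% type I error depend entirely on assumed exclusions in one arm only and an assumed 0.5 to 1.0 SD difference. The matter should be fixed, at the low end of that grade.

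**What to change.** - **5.7.1.** State that participants over the nights-away threshold stay in follow-up unless they withdraw consent, that the final blood draw already scheduled is sought within the 7.6 window (35 − 28 = 7 days beyond four weeks), and that their TNFα is analysed under intention-to-treat in the arm first assigned. This concerns follow-up and analysis only. It does not prescribe how the device is used around an absence.
- **Threshold.** Reconcile 5.7.1, which counts two or more nights in a row, with inclusion criterion 8 in 5.1, which counts more than 48 hours in a row. Two nights away can span less than 48 hours. Both also use a seven-day total.
- **10.2.** Once the threshold is settled, add nights away to the per-protocol definition and report that analysis as a sensitivity analysis.
- **Aim 2.** Report results with and without participants over the threshold.
- **Re-enrolment.** Delete it, or state that only the first randomisation is analysed.
- **Consistency.** Align 7.7 (withdrawal visit) and 10.4 (baseline-only data) with the new wording.

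The cost is text in a few sections and no new visit. The downside is some dilution of the intention-to-treat effect, 0.6 to 2.3% of its size if 2 of 22 are away for 2 to 7 nights and more if absences are longer or more frequent. The per-protocol sensitivity analysis would help to show it. Participants who still give no final sample remain missing data, which this wording alone does not resolve.

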5.7.2 Handling of Participant Withdrawals or Termination

Participation is voluntary and all study participants may withdraw from the study at any time without penalization. Participants may request removal and destruction of their blood samples from storage for future research without withdrawal from the remainder of the study. Participants may request termination from the study separate from withdrawal from future research.

No replacement of participants who withdraw or discontinue early will occur. Data including date and reason for withdrawal will be recorded.

A participant is considered lost to follow-up after 10 attempts to contact them by phone and 10 attempts by Epic messaging.

5.7.3 Premature Termination or Suspension of Study

This study may be suspended or prematurely terminated if there is sufficient reasonable cause. Written notification, documenting the reason for study suspension or termination, will be provided by the suspending or terminating party to the study principal investigators ([name], [name]). If the study is suspended or prematurely terminated the PIs will promptly inform the IRB and will provide the reason(s) for the termination or suspension.

Circumstances that may warrant termination or suspension include, but are not limited to:

- Insufficient compliance to protocol requirements
- Loss of institutional political will to examine health effects of the national policy
- Determination that the study procedures are too invasive

Study may resume once concerns about safety, protocol compliance, data quality are addressed and satisfy the sponsor and/or IRB.

6 Study Agent (Study drug, device, biologic, vaccine etc.) and/or Procedural Intervention

This study will utilize a portable air cleaner as an intervention for the potential reduction of air pollution-associated inflammation. This commercially available device has no significant risks. We plan to use a commercially available PAC with a “true HEPA” filter for the true arm. For the sham arm, the same model will be used with HEPA filter removed, and has identical appearance and sound. We will use a PAC designed to filter air in rooms up to approximately 350 ft², with minimal noise on the lowest setting.

6.1 Study Agent(s) and Control Description

This study will utilize a sham PAC as a control. PAC will be delivered to participants as active or sham PAC in blinded fashion. The study team will receive the new devices and remove filters from sham PACs. Filters will be stored in our research office until the participant completes the protocol, at which time participants will return study equipment at receive filters to keep. Filter status indicator lights on the PAC will be covered with black electrical tape on all devices (active and sham) to preserve blinding.

6.1.1 Acquisition

PACs will be ordered online and delivered to the study team research office for preparation.

6.1.2 Formulation, Appearance, Packaging, and Labeling

This is a commercially available product and will be delivered to participants in original packaging, which will have been opened to prepare and blind devices.

6.1.3 Preparation

Commercially available PACs contain carbon filters that reduce volatile organic carbons and can reduce odors. Because of this, we will remove the carbon filters from all air purifiers to preserve blinding. Sham PACs will also have HEPA filters removed. This will be done by unblinded research staff and devices will be labelled with an ID number to preserve blinding of the rest of the research team.

6.1.4 Duration of Therapy

The PACs will be run continuously (24 hours per day) in participants' bedrooms for 4 weeks.

7 Study Procedures and Schedule

7.1 Study Procedures/Evaluations

7.1.1 Study Specific Procedures

History will be obtained via participant medical records and confirmed with questionnaire. Medical comorbidity information collected will include: history of hypertension, duration of hypertension, history of diabetes; history of inflammatory conditions including Crohn's disease, ulcerative colitis, rheumatoid arthritis, vasculitides such as Kawasaki disease and giant cell arteritis, cancer and current status (no evidence of disease, ongoing treatment, cured, etc). We will also collect current prescription medications and assess for any planned medication changes during the study period. We will collect blood pressure, BMI and waist circumference at the initial visit. We will collect <15 mL of blood for evaluation of inflammatory biomarkers at both the initial visit and the final visit. An additional ~10 mL of blood will be drawn from participants opting in to storage for future research.

7.1.2 Standard of Care Study Procedures

Regular standard of care procedures will be performed by clinical providers at the initial clinical visit and data will be recorded to RedCAP for research purposes by research staff at the time of enrollment. These data include measurement of blood pressure, height and weight and waist circumference. Medication reconciliation performed for the clinical visit will be confirmed by research staff as well.

7.2 Laboratory Procedures/Evaluations

7.2.1 Other Assays or Procedures

We will evaluate biomarkers of inflammation using the Olink Explore 384 Cardiometabolic panel. This panel will be performed by Olink. The Olink analysis uses a Proximity Extension Assay that has been shown to have high specificity and accuracy to allow for assessment of changes in concentrations between repeated samples over time.

7.2.2 Specimen Preparation, Handling, and Storage

Blood samples will be processed for both cardiometabolic biomarker measurement and storage for future research. Samples for Olink will be collected into EDTA coated tubes and centrifuged within 1 hour and samples will be placed in 96-well PCR plate (ThermoFisher Scientific #AB0800 with MicroAmp seal #4306311 from ThermoFisher Scientific). Samples will be randomized within plates using random-number generator and stored at -80C until shipped on dry ice to Olink for analysis of biomarker concentrations. Olink will not receive any participant identifying information. The remainder of blood will be stored in a secured laboratory in the Cardiology Division Science Building Laboratories.

7.2.3 Specimen Shipment

Specimens will be stored at -80C until shipped on dry ice to Olink when 96-well plates are filled until all data is collected. After all data is collected, remaining specimens for participants who have not opted in to future research will be discarded by the lab.

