Population	We will perform a randomized, double-blind, sham-controlled trial of continuous (24 hours/day) bedroom PAC use in an outpatient cohort English and Spanish speaking adults ≥ 18 years of age with stable hypertension (defined as no medication changes in prior 30 days, systolic BP < 160 mm Hg and either ≥ 130 mm Hg without antihypertensive medications, or diagnosis of hypertension in medical records). Per guidelines, this range is considered safe to monitor without changes in antihypertensive medications. Additional inclusion criteria require participants to measure home blood pressure twice daily, participate in video conference for home equipment setup, and ability to visit clinic for blood draws before and after the study period. Participants will be excluded if they are current smokers, currently have known coronary artery disease, have known systemic inflammatory conditions (such as rheumatoid arthritis, inflammatory bowel disease, cancer), or are currently taking any anti-inflammatory medications or medications that target inflammatory cytokines. We aim to enroll 44 participants, randomized in a 1:1 ratio to PAC with HEPA filtration versus sham filtration.

Study Sites	Participants will be consented and enrolled at NYU outpatient clinic facilities in Manhattan. At this visit, patients will have baseline blood drawn and will receive all study equipment. Participants will set up air pollution monitor and PAC in their homes with video chat guidance. PAC will be run continuously in participant bedrooms for 4 weeks. Participants will have follow-up visit to NYU Langone hospital clinical lab for post-intervention blood collection and equipment return.
Number of participants	To achieve 44 study participants, we will need to identify \approx 300 eligible participants from the electronic health record (EHR) in NYU clinics. There will be 22 participants per arm (sham versus active filtration).

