4.1 Description of Study Design

In this research, we will conduct a randomized, double-blind, sham-controlled pilot trial to study the effect of PAC use on the concentrations of circulating biomarkers of inflammation in outpatient adults within the NYU Langone Health system.

Aim 1: To determine if 4 weeks of home air filtration with PACs compared to sham is associated with significant reductions in TNF α concentrations when measured before and after intervention.

Data collection will begin Q2 2022 with a total of two time points 4 weeks apart, pre- and post-intervention. The study design utilizes purposeful selection of 74 adults with stable hypertension within the NYU Langone health system outpatient cohort. We will define stable hypertension as no medication changes in prior 30 days, systolic BP <160 mm Hg and either \geq 130 mm Hg without antihypertensive medications, or diagnosis of hypertension in medical records. Per guidelines, this range is considered safe to monitor without changes in antihypertensive medications. At the initial clinic visit, blood will be collected and stored for analysis. We will measure circulating concentrations of TNF α using the Olink Explore 384 Cardiometabolic panel for this *a priori* specified analysis; this panel will also measure the concentrations of other biomarkers that we will explore further in Exploratory Aims 1 and 2. The Olink analysis uses a Proximity Extension Assay that has been shown to have high specificity and accuracy to allow for assessment of changes in concentrations between repeated samples over time.^{18, 19}

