10.4 Sample Size

Power Analysis: While we do not expect substantial participant dropout over this short trial, our power analyses include adjustment for up to 10% dropout in each arm. Based on our meta-analysis of biomarkers²², we estimate a 10% change in concentration of biomarkers with PAC use versus sham.^{13 13} Using a basic multiple regression model incorporating age, BMI, and gender, along with our exposure (active PAC vs sham), we will have greater than 80% power to reject the null hypothesis of zero effect size at the significance level (alpha) of 0.05, with a sample size of 66. As such, our enrollment goal of 44 participants, limited by budgetary constraints, may provide sufficient power to detect significant changes in biomarker concentrations. However, in the event that we are not able to reach statistical significance with the changes we detect, these results will still be informative for developing future studies. We will include baseline-only data for participants who do not complete the protocol.

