10.5 Measures to Minimize Bias

10.5.1 Enrollment/Randomization/Masking Procedures

We will block randomize participants for a net 1:1 allocation to active- versus sham-PAC arms. We will have one unblinded PI and one unblinded research coordinator; the remainder of the research staff will be blinded to each participant's treatment arm until the final visit (at which time, those in the sham PAC arm will receive HEPA filters). The allocation sequence file will be securely stored in an internal NYU OneDrive in a password protected file to which only the unblinded PI and unblinded research coordinator will have access.

PAC devices will be modified by unblinded research coordinator and/or unblinded PI; all PACs will have indicator lights covered, sham-PACs will have HEPA filters removed. PACs will be assigned a tracking ID number that will be printed on PACs, and PAC boxes. Blinded staff will only know the PAC ID number assigned to a participant but not the randomization of the device.

Unblinded research coordinator and PI will assess enrollment goals.

Blood samples will be assigned to PCR plate locations using a random number generator.

Data from PM monitors will be downloaded after participant has completed protocol. Research team members performing data processing of PM measurements will be blinded to PAC status of participant.

11 Source Documents and Access to Source Data/Documents

Source data include all study-related forms, including: completed surveys, checklists, interview transcripts, consent forms, air monitor documentation, and study personnel tracking sheets. Access to study records will be limited to IRB-approved members of the study team. The investigator will permit study-related monitoring, audits, and inspections by the IRB/EC, the sponsor, government regulatory bodies, and University compliance and quality assurance groups of all study related documents.

Participation as an investigator in this study implies acceptance of potential inspection by government regulatory authorities and applicable University compliance and quality assurance offices.

12 Quality Assurance and Quality Control

QC procedures will be implemented beginning with the data entry system and data QC checks that will be run on the database will be generated. Any missing data or data anomalies will be communicated to the site(s) for clarification/resolution.

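### If 74 participants are enrolled, nothing keeps a participant's two samples on one plate, so plate differences would add avoidable noise to the TNFα change

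*Combined protocol and SAP*

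**What the plan says.** **Endpoint and model.** Section 4.2.1 defines the primary endpoint as the percent change in TNFα from before to after the intervention. Section 10.3 models that change on arm, age, gender and BMI. It has no term for plate or assay batch.

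**Sample handling.** Three sentences bear on plate layout:
- Section 7.2.2: "Samples will be randomized within plates using random-number generator".
- Section 10.5.1: "Blood samples will be assigned to PCR plate locations using a random number generator".
- Section 7.2.3: specimens are "shipped on dry ice to Olink when 96-well plates are filled until all data is collected".

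The first two deal with position and the third with timing of shipment. None says which plate a sample goes to, and no bridging samples are described.

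**Enrolment.** Section 4.1 speaks of "purposeful selection of 74 adults with stable hypertension", and section 5.6 states "Recruitment will end when we have consented and enrolled 74 adults, of which we expect 90% to complete the trial". Section 10.4 refers to "our enrollment goal of 44 participants, limited by budgetary constraints". The Protocol Summary and section 5.4 also give 44.

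**The concern.** When both samples of a participant are assayed on one plate, a shift shared by that plate drops out of the within-person comparison: a multiplicative shift cancels from the ratio behind a percent change, and an additive one from a difference of logs. When the samples are on different plates, the difference between plates is added to that person's change. It then enters the residual variance of the primary analysis and the change in every panel protein in Exploratory Aim 1.

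Shipping plates as they fill makes splitting likely once one plate is not enough. Early participants have both samples on the first plate, late participants have both on the second, and those in between have baseline on the first and follow-up on the second. Once the first plate has been shipped and assayed, the layout cannot be changed. Section 10.4 already says only that 44 may give sufficient power, so noise that can be avoided at almost no cost is worth avoiding.

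**Working it through.** **1. Enrolment figure.** Section 10.4 gives 66 required and up to 10% dropout. 66 / (1 − 0.10) = 73.3, rounded up to 74. This reproduces sections 4.1 and 5.6. The 66 itself cannot be reproduced, because no SD or R² is stated.

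**2. Number of plates** (two samples each, 96 wells):
- 44 × 2 = 88, which fits one plate with 8 wells spare. No pair can be split.
- 74 × 2 = 148, which needs two plates. With 66 completers it is 74 + 66 = 140, still two.

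**3. Split pairs at 74.** The samples were sorted by draw date, with the first 96 on plate 1 and the rest on plate 2. Assumptions: even accrual and 4.5 weeks between draws. The visit windows in sections 7.5 and 7.6 allow up to 7 + 35 = 42 days, or 6 weeks. The accrual period is not stated. Section 7.3.1 looks for clinic visits in two quarters of 2022, about 26 weeks, so 13 to 39 weeks brackets that. The results are 26 split pairs at 13 weeks, 12 at 26 weeks and 8 at 39 weeks. With a 6-week gap they are 34, 18 and 12.

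**4. Baseline SD.** With 33 per arm, two-sided α = 0.05, a 10-point difference and 80% power, the noncentral t gives SD = 14.28 points, so the variance is 203.9. This is back-solved, not a figure from the documents.

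**5. Added variance.** In draw-order filling, every split pair has baseline on plate 1 and follow-up on plate 2, so the offset d has the same sign in all of them. With a proportion p split, the added variance is p(1 − p)d². The documents give no plate offset, so d = 5, 10 and 15 points are assumptions. The offset is treated as additive on the percent-change scale, which is an approximation.

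| Accrual | Split | p | p(1 − p) | d = 5: variance, power | d = 10: variance, power | d = 15: variance, power |
|---|---|---|---|---|---|---|
| 39 weeks | 8/74 | 0.108 | 0.096 | +1%, 79.5% | +5%, 78.2% | +11%, 75.9% |
| 26 weeks | 12/74 | 0.162 | 0.136 | +2%, 79.4% | +7%, 77.4% | +15%, 74.3% |
| 13 weeks | 26/74 | 0.351 | 0.228 | +3%, 78.9% | +11%, 75.7% | +25%, 70.7% |

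Example for 13 weeks and d = 10: 0.228 × 100 = 22.8, and 22.8 / 203.9 = 11%. The SD becomes √(203.9 + 22.8) = 15.06, and power at 66 is 75.7%.

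**6. Upper limit.** Because p(1− p) cannot exceed 0.25, the inflation at d = 10 cannot exceed 25 / 203.9 = 12%, however fast accrual is.

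The split proportion is counted over 74 pairs and power over 66 completers. This mismatch is small beside the uncertainty in d.

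**The case against.** **The problem may never arise.** The Protocol Summary, section 5.4 and section 10.4 all give 44, and section 10.4 attributes that figure to budget. At 44 one plate is enough unless more than 8 wells are reserved, and the documents reserve none. This stands, and it makes the point conditional. It does not remove it: sections 4.1 and 5.6 state 74 in the current text, and section 7.2.3 speaks of plates in the plural. The plural alone does not settle which figure applies.

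**The offset may be small.** The assay is run by an outside laboratory (section 7.2.1). Any normalisation between plates is not described, and it would shrink the effect, possibly to near nothing. This also stands, so the power figures are illustrations only.

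**Draw-order plating is inferred.** The sentence quoted from section 7.2.3 is about shipment. Filling plates in order of draw is the natural reading alongside section 7.2.2, but it is not stated.

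**A larger loss is tempting to infer.** A reader might take the random number generator to scatter samples across both plates. That would split 2 × 96 × 52 / (148 × 147) = 46% of pairs, 34 of 74. Offsets would then take both signs, and a 10-point offset would raise variance by 23% and cut power to 72%. The documents do not support this: section 7.2.2 randomises within plates, section 10.5.1 speaks only of locations, and scattering across plates is hard to combine with shipping each one as it fills.

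**Conclusion.** The point holds as a conditional and minor one. The plan has no rule that keeps pairs together and no plate term. At 74 enrolled, following it as written would split some pairs; at 44 it would not.

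Under draw-order filling, the expected loss at 66 evaluable is from 80% power to about 78–76% for a 10-point offset, about 79% for 5 points and about 76–71% for 15 points. These figures rest on an assumed accrual period, draw gap and offset, and on a back-solved SD.

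A reader might also infer that the one-directional shift biases the treatment effect. The documents do not support that for the primary contrast. Arms are block-randomised 1:1 and most staff are blinded (section 10.5.1), so whether a pair is split should not depend on arm, and a shift common to both arms cancels in expectation. What is lost is precision.

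**What to change.** 1. Reconcile 44 and 74 across the Protocol Summary and sections 4.1, 5.4, 5.6 and 10.4. The number of plates follows from this.
2. State in sections 7.2.2, 7.2.3 and 10.5.1 that both samples of a participant go on the same plate, that wells are randomised within the plate, and that a plate is shipped only when it consists of complete pairs. Baseline-only samples go on the last plate. At 74 this still takes two plates, for example 48 + 26 pairs, with none split.
3. If more than one plate is used, either balance arms across plates through a coded list, so that laboratory handling stays blinded, or add a plate term to the section 10.3 model.

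The cost is small. Baseline samples are held at −80C until the pair is complete, and the first plate ships somewhat later. Storage at that temperature until shipment is already planned. Balancing by arm adds one coded list, prepared by someone who already holds the allocation.
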